9.5 Sequence of Assessments

During treatment visits (Visit 2 to 7), following sequence of assessments should be followed at the site:

- Patient related questionnaire DLQI filling
- PASI, involved BSA and IGA assessment by Independent dermatologist
- PASI, involved BSA and IGA assessment by investigator
- Clinical examination, vitals, medical history, concomitant medication, AE assessment, photography and other study related procedures mentioned in Table 1
- IP compliance check (Visit 3 onwards)
- IP dispense according to IWRS
- Dosing at the site followed by PK sampling in consenting patients at week 4 (±2 days) visit.

10.0 ADVERSE EVENTS

10.1 Definition of Adverse Event

An AE is defined as any untoward medical occurrence in a subject administered a pharmaceutical product and which does not necessarily have a causal relationship with this treatment. An AE can therefore be any unfavorable and unintended sign (including an abnormal laboratory finding), symptom, or disease temporally associated with the use of a medicinal (investigational) product, whether or not related to the medicinal (investigational) product.

Changes in clinical laboratory test results, vital signs and ECG results are to be recorded as AEs if they are judged to be clinically significant.

Pre-planned or elective surgeries should be avoided during the conduct of the study. Pre-planned or elective surgeries or therapies should be recorded in the patient's source documents but are not be considered AEs unless there is any change to the patient's medical condition.

SAE is defined as any untoward medical occurrence that at any dose:

- results in death;
- is life threatening;
 - requires inpatient hospitalization or prolongation of an existing hospitalization; results in persistent or significant disability/incapacity; Day care or outdoor surgery/procedure (e.g. stenting, Ryle's tube insertion, tracheostomy cleaning, wound care, etc.) for prevention of any complication will not be considered as SAE but event leading to such procedure should be recorded as AE (if arise during the study period) or in medical history (if pre-existing condition)
 - Any planned hospitalization, such as hospitalization for PK sampling, will not be considered SAE.

Note: Complications that occur during hospitalization are adverse events and if a complication prolongs hospitalization, then the event is serious;

- results in a congenital anomaly/birth defect;
- results in another important medical event that may not be immediately life threatening or does not result in death or hospitalization, but which may jeopardize the subject or may require medical or surgical intervention to prevent one of the outcomes listed above.

Examples of important medical events which may meet the definition of a SAE include: intensive treatment in the emergency room or at home for allergic bronchospasm, certain abnormalities (e.g., blood dyscrasias), convulsions that do not result in hospitalization, or the development of drug dependency or drug abuse.

10.1.1 Recording and follow-up

For each patient, all AEs will be collected from informed consent through to the follow-up visit. AE assessment will be continuous throughout the study period.

Pre-existing conditions (present at or before screening day; they will be recorded in medical history) are only to be recorded as AEs if the patient experiences a worsening or complication of the condition, and the description recorded in the CRF should clarify this. The onset of such an AE should correspond to the onset of the worsening of the pre-existing condition.

For each AE, the following information will be recorded:

- AE description/term
- Treatment start and stop dates and times
- Frequency i.e. single episode or intermittent
- Severity: mild (easily tolerated), moderate (interferes with daily activities) or severe (prevents normal daily activities)
- Relationship to study drug (definite, probable, possible, unlikely or not related)
- Outcome (resolved, resolved with sequelae, or ongoing)
- Whether serious or not

Definitions for the relationship to study drug assessment, to be made by the investigator, are as follows:

- **Definitely related:** This category applies when, after careful medical consideration, there is almost no consideration of other causation.
- **Probably related:** There is a clinically plausible time sequence between onset of the AE and study treatment administration. The AE is unlikely to be caused by a concurrent and/or underlying illness, other drugs, or procedures. If applicable, the AE follows a clinically consistent resolution pattern upon withdrawal of study drug.
- **Possibly related:** There is a clinically plausible time sequence between onset of the AE and study treatment administration, but the AE could also have been caused by the concurrent/underlying illness, other drugs, or procedures. Information regarding study drug withdrawal may be lacking or unclear. "Possible" should be used when study treatment administration is one of several biologically plausible causes of the AE.
- **Unlikely related:** The AE is most likely due to a non-study-treatment-related cause. However, association with the study treatment cannot be completely ruled out.
- **Unrelated:** Another cause of the AE is most plausible, and a clinically plausible temporal sequence is inconsistent with the onset of the AE and study treatment administration and/or a causal relationship is considered biologically implausible.

For the purpose of regulatory reporting requirements, causal relationships of definite, probable, and possible will be considered treatment-related, while unlikely and unrelated will be considered not treatment-related.

All AEs should be followed up until the AE resolves or the investigator considers that further follow-up is not necessary.

Severity will be assessed by the investigator and will be graded as mild, moderate or severe.

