The study did not reveal any clinically relevant hepatic, renal, cardiac, respiratory, or neurological adverse events at any of the dosages in SAD. MAD and Comparative PK cohorts. There is no evidence of any remarkable effect of AUR101 on any clinical laboratory parameters, including hemoglobin, blood counts, liver function or kidney function or on ECG, vitals or physical examination. There were two cases of altered liver function parameters, one occurred in placebo treated subject (Grade 2) in MAD cohort and the other one in comparative PK part with open label AUR101 film coated tablet (Grade 1). Both of these events were deemed as related by the investigator, resolved and did not require any intervention. There were no Grade 3 or higher AEs or serious adverse events (SAEs) or any interruption or discontinuation of the study drug due to AE.

Most commonly reported non-catheter associated Treatment-Emergent Adverse Events (TEAEs; reported ≥ 2 subjects receiving any dose of AUR101 or placebo) in SAD part were fatigue, headache, dizziness, nausea, vomiting, arthralgia, cough and backpain. In MAD part, most commonly reported non-catheter associated TEAEs were headache, abdominal pain, abdominal distension, abdominal discomfort, diarrhea and back pain. In comparative PK part, only headache was reported in ≥ 2 subjects. All of the AEs were mild to moderate in nature and resolved to the satisfaction of the PI. There was no relevant difference between placebo and the AUR101 arms with respect to the nature, severity or frequency of AEs. There is also no pattern or relationship of AEs with AUR101 dose, schedule or formulation.

The study findings from SAD cohorts also confirm that AUR101 is primarily absorbed in the stomach and minimal from intestine. Moreover, food increases the exposure by \sim 2.5 times, further re-confirming that retention of AUR101 in stomach leads to increased absorption.

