11.7.3 Clinical Laboratory Tests

Clinical laboratory test results will be summarized by treatment groups using descriptive statistics and will include hematology, chemistries, and urinalysis. Laboratory test values which are outside the normal range will be flagged as H (above high normal limit), L (below low normal limit), or A (abnormal) in the data listings. Laboratory values deemed clinically significant by the Investigator should be reported as AEs.

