### 8.1 Adverse Events

AEs will be coded using the Medical Dictionary for Regulatory Activities (MedDRA). The number and percentages of patients experiencing AEs will be tabulated by system organ class (SOC), preferred term, maximum severity, and relationship to AUR101. Summaries of the number of patients with DLTs, dose reductions/interruptions, SAEs, treatment-related AEs, AEs resulting in treatment/trial discontinuation, and deaths will be presented by dose cohort.

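### The AE severity scale has no criterion for symptom-free laboratory events, and no planned table counts patients in each arm by the size of a liver-enzyme rise

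*Protocol*

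**What the plan says.** **Which findings become AEs.** Protocol 10.1: "Changes in clinical laboratory test results, vital signs and ECG results are to be recorded as AEs if they are judged to be clinically significant". Protocol 11.7.3 repeats this for laboratory results: "Laboratory values deemed clinically significant by the Investigator should be reported as AEs".

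**How an AE is graded.** Protocol 10.1.1 lists the item as "Severity: mild (easily tolerated), moderate (interferes with daily activities) or severe (prevents normal daily activities". The same section closes with "Severity will be assessed by the investigator and will be graded as mild, moderate or severe" and adds no further criterion.

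**Where the grade goes.** SAP 8.1, in the same terms as Protocol 11.7.1: "The number and percentages of patients experiencing AEs will be tabulated by system organ class (SOC), preferred term, maximum severity, and relationship to AUR101".

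**What else is planned for laboratory data.** SAP 8.5 provides:
- n, mean, SD, SE and median (IQR) by group;
- descriptive statistics for change from baseline;
- shift tables classed as normal or abnormal (clinically significant or not), produced for all patients together without identifying the arm.

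Protocol 11.7.3 adds high, low and abnormal flags in the listings.

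Neither document sets out a laboratory grading scale or a post-baseline category in multiples of ULN. The only ULN multiple is the 1.5-fold eligibility limit in exclusion criterion 10.

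**The concern.** The severity scale was written for symptoms. A raised ALT without symptoms neither interferes with daily activities nor prevents them, so the wording leaves it one place to go, however large the rise. The maximum-severity table is where a reader of the report will look for the seriousness of the liver picture in each arm, and on this scale it may carry no information about size.

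This matters because liver enzymes are a known point of interest in the sponsor's own data. Protocol 3.2.3 reports AST/ALT increases in the 13-week dog study at 30 mg/kg BID (the NOAEL) and above. Protocol 3.4.1 puts exposure at that NOAEL 2.5-fold above human exposure at 600 mg BID. The same section says two doses are studied to weigh the risk and benefit of each and to help choose the Phase III dose. For that purpose it helps to know how many patients on each dose had a small, moderate or large rise.

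**Working it through.** The plan states no figure to reproduce, so the check is of the text, followed by one labelled illustration.

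**Step 1: can a symptom-free laboratory event meet each category?**
- Mild requires that it be easily tolerated: yes.
- Moderate requires interference with daily activities: no.
- Severe requires that it prevent normal daily activities: no.

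The result does not depend on the size of the rise. An investigator who grades a large rise higher is using a criterion the protocol does not supply, and the synopsis plans 15-25 centres.

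**Step 2: does another planned output give size by arm?**

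| Output | By arm? | Gives size of rise? |
|---|---|---|
| AEs by SOC and preferred term (SAP 8.1) | Yes | No, incidence only |
| AEs by maximum severity (SAP 8.1) | Yes | Not reliably (step 1) |
| SAEs, related AEs, AEs leading to discontinuation (SAP 8.1) | Yes | No, separate attributes |
| Laboratory shift tables (SAP 8.5) | No, pooled | No, normal/abnormal and clinical significance |
| Laboratory summaries by group (SAP 8.5) | Yes | Mean and median only; no maximum, no ULN multiple |
| Flags in listings (Protocol 11.7.3) | Patient level | No, direction only |

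No row counts patients in each arm by size of rise.

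**Step 3: illustration (hypothetical counts).** Take 30 patients per arm, the planned number. Suppose 2 on 600 mg have a symptom-free ALT of 8 times ULN and none on placebo do.
- Incidence by preferred term: 2/30 = 6.7% v 0/30. The difference between arms is visible.
- Maximum severity, read literally: mild 2, moderate 0, severe 0 on 600 mg; all 0 on placebo.
- If the same two patients had instead risen to just above 1.5 times ULN and both were recorded as AEs, both tables would be identical.

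Now the by-group summary. Assume further that both patients start at 1 times ULN, that both peaks fall at the same visit, and that the other 28 do not change.
- Mean change for two rises to 8 times ULN: 2 × (8 − 1)/30 = 0.47 times ULN.
- Mean change for two rises to 1.5 times ULN: 2 × (1.5 − 1)/30 = 0.03 times ULN.
- Median change in both cases: 0.
- If the two peaks fall at different visits, the larger mean shift halves: 7/30 = 0.23 times ULN.

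The mean moves, but it cannot tell two large rises from many small ones. For example, a rise of 0.47 times ULN in all 30 patients gives the same mean.

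**The case against.** **Severity is a judgement, and neither document says these events are mild.** A reader might infer that every symptom-free laboratory AE will be recorded as mild. The documents do not say so. Protocol 10.1.1 leaves the grade to the investigator, so the supportable statement is that the scale gives no criterion, with mild as the literal outcome.

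**The arms can still be told apart.** This is right. The table by SOC and preferred term would show 2 v 0. SAEs, related AEs and discontinuations are shown by dose, and a large rise can be reported as an SAE under the important-medical-event criterion in Protocol 10.1 whatever its severity. What is lost is size, not the existence of a difference.

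**The liver evidence is modest.** It would be tempting to call a silent enzyme rise the harm this drug is most likely to cause. Protocol 3.2.3 describes the 30 mg/kg BID rise as mild, reversible and non-adverse, and the adverse rises came at doses that also produced clinical signs. Protocol 3.3 reports no remarkable laboratory effect in Phase I. Of its two liver-function cases, the Grade 2 was on placebo and the Grade 1 on AUR101. Liver tests deserve a proper table, but the documents do not rank the risk.

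**Phase I comparability.** Protocol 3.3 uses numeric grades ("There were no Grade 3 or higher AEs or serious adverse events (SAEs") but names no scale and does not say that the grades came from numeric limits. It also describes the AEs as mild to moderate. One cannot conclude that the two studies cannot be compared, only that the scale is not carried forward here.

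**Maxima.** Protocol 11.4.1 includes minimum and maximum in its general list of summary statistics; SAP 8.5 leaves them out. If the protocol list is followed, the single worst value per visit would appear by arm. That helps, but it still does not count patients.

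**ECG.** The same gap exists on paper for ECG events. It has little reach, because scheduled ECGs are only at Screening and Follow-up (Protocol 9.2.4).

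**Cost.** Rewriting 10.1.1 would be an amendment needing IRB/EC approval (Protocol 12.5), and replacing recorded severities would override the investigator. Both objections stand, so the change belongs in the SAP and beside the recorded severity.

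**Conclusion.** The point holds as a gap in reporting. The severity scale has no criterion for symptom-free laboratory AEs, so the maximum-severity table does not reliably convey the size of a liver-enzyme rise. No other output in the SAP counts patients by size in each arm. The effect is on the dose-specific safety comparison. It does not touch the primary analysis, the type I error or the power, and no number in the plan is wrong.

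The size cannot be stated as a figure, because it depends on how many such rises occur and how investigators grade them. If there are none, nothing is lost. If there are a few, their incidence will be seen and their magnitude will have to be found in the listings. The conclusion rests on two assumptions: that no grading rule exists outside these documents (for example in CRF completion guidance), and that SAP 8.5 is the full laboratory output.

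**What to change.** Leave Protocol 10.1.1 and the investigator's severity as they are. In SAP 8.1 and 8.5:

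1. Name one magnitude-based laboratory grading scale: the one used in AUR101-101 if that was numeric, otherwise one the sponsor states.
2. Derive each patient's worst post-baseline grade and tabulate it by treatment arm, at least for ALT, AST, ALP and total bilirubin. State that repeat and unscheduled values count. Under SAP 5.4 a repeat is used only where the scheduled value is missing, so a higher repeat could otherwise drop out.
3. Present the laboratory shift tables by arm instead of pooled.
4. For AEs that are laboratory findings, report the derived grade beside the investigator's severity.
5. Restore the minimum and maximum listed in Protocol 11.4.1 to the laboratory summaries.

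The values are already collected at Screening, Day 1, Weeks 4, 8 and 12 and Follow-up (Protocol 9.2.3), so there is no new test or visit. The cost is one derivation, one additional table and a change of layout. The downside is that some events recorded as mild will also carry a higher laboratory grade, which the report will need to explain. The change should be made before unblinding, since SAP 1.0 requires analyses outside the plan to be labelled as unplanned.

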10.1.2 Procedures for reporting SAEs

All SAEs, regardless of relationship to the study treatment, must be reported to the Sponsor or designee within 24 hours of the Investigator becoming aware of the event. Written SAE notification must follow within the 24-hour reporting timeframe, via an SAE Report submitted to the Sponsor's medical monitor via e-mail ID provided in Appendix A. Follow-up SAE reports must be submitted by the Investigator as new information becomes available. All treatment related SAEs should be followed until resolution, return to baseline, or stabilization.

If the investigator becomes aware of safety information involving a patient who participated in the study that appears to be drug related, even after an individual patient has completed the study, this should also be reported to the Sponsor immediately.

Sponsor will provide compensation for any drug related injury/death and medical management cost for drug related AEs, for a patient enrolled in India, according to applicable Central Drugs Standard Control Organization (CDSCO) regulations and as ordered by CDSCO, India.

10.1.3 Reporting to the IRB / ECs

SAEs will be reported to the local Institutional Review Board (IRB) / EC by the Investigator as per regulatory and IRB requirements. Sponsor will also report to IRB/IEC as per applicable regulations

10.1.4 Reporting to the Regulatory Agency

The Sponsor will be responsible for reporting all AEs and SAEs to the appropriate regulatory authority (e.g., U.S. Food and Drug Administration, CDSCO etc.) in accordance with respective guidelines.

Investigators, and IRB/EC in accordance with all applicable local regulations and guidance.

10.2 Pregnancy Reporting

Pregnancy testing must be performed in all female patients of childbearing potential throughout the study as specified in the Schedule of Events (Table 1), and the results of all pregnancy tests are to be recorded. In the event of a confirmed positive test

result, patients will be discontinued from study drug and will be followed for the outcome of their pregnancy.

If a female patient suspects she might be pregnant (e.g., missed or late menstrual period) or a male patient suspects he may have fathered a child at any time during the study through the Follow-up visit, they must notify the Investigator immediately. The Investigator will follow the patient or patient's partner to determine the outcome of the pregnancy.

Information regarding pregnancy must be reported immediately to the Sponsor and the outcome information provided once the outcome is known. The Sponsor will be responsible for reporting all pregnancy cases to the appropriate regulatory authority (e.g., U.S. Food and Drug Administration, CDSCO etc.), Investigators, and IRB/EC in accordance with all applicable local regulations and guidance.

11.0 DATA MANAGEMENT AND STATISTICAL ANALYSIS

11.1 Sample Size Calculation

AUR101 doses will be tested versus placebo with respect to the primary endpoint (PASI75 response). A sample size of 25 in each of the three arms will provide an 80% power with a one-sided Type I error of 0.05, if the true placebo response rate is 7% and the response rate on investigational arm(s) is 35%. The sample size is increased to 30 to account for \sim 15-20% drop outs over the study period.

Placebo response rates from previous studies was 4-7% in most of the studies in similar patient population [17-19].

11.2 Data Handling

Data obtained in this study will be collected in eCRFs prepared by sponsor/designee. The eCRF will be completed and monitored in accordance with the principles of GCP.

Source data is defined as all information in original records and certified copies of original records of clinical findings, observations, or other activities in a clinical trial necessary for the reconstruction and evaluation of the trial. Source documents are original documents, data and records, such as laboratory printouts, 12-lead ECG reports, dispensing records, and patient files. In case, any data is recorded directly into the eCRFs, then that will be considered as source and should be appropriately reflected in the study records.

AEs, medical history, and pre-existing (concurrent) conditions will be coded using the Medical Dictionary for Regulatory Activities (MedDRA). Drugs will be coded using the World Health Organization (WHO) Drug Dictionary (WHO-DD).

11.3 Analysis Sets

11.3.1 Safety Population

The Safety Population includes all patients in the study who receive at least one dose of AUR101.

11.3.2 Efficacy Population

Efficacy population will include patients who do not have any major protocol or inclusion/exclusion violations, have a valid baseline and at least one post-baseline (follow up) assessment for PASI score by the independent dermatologist.

11.3.3 Pharmacokinetic Population

The Pharmacokinetic Population includes all patients in the study who receive any dose of AUR101 and provide samples for PK analysis.

11.4 Description of Statistical Analyses

11.4.1 General Considerations

Data will be summarized using descriptive statistics (number of patients, mean, median, standard deviation, minimum, and maximum) for continuous variables and using frequencies and percentages for discrete variables. Data will be presented by treatment arms.

A comprehensive statistical analysis plan (SAP) will be finalized prior to final data analysis.

11.4.1.1 Medical history

Any condition entered as medical history or current medical conditions at baseline will be coded using the MedDRA dictionary. They will be summarized by system organ class and preferred term of the MedDRA dictionary.

11.4.1.2 Prior and concomitant medication

Prior and concomitant medications will be summarized by treatment group in separate tables.

Prior medications are defined as treatments taken and stopped prior to first dose of study treatment. Any medication given at least once between the day of first dose of randomized study treatment and the last day of study visit will be a concomitant medication, including those which were started pre-baseline and continued into the treatment period.

Medications will be coded by WHO-DD.

